Short-term Efficacy of Chlorhexidine and Povidone-Iodine Mouth Rinses in Reducing Salivary SARS-CoV-2 Viral Load: A Randomized Controlled Clinical Trial

NCT04941131

June 24, 2021

[name]

1. Background and Rationale

Severe Acute Respiratory Syndrome Coronavirus 2 (SARS-CoV-2) is primarily transmitted through respiratory droplets and aerosols. Dental procedures pose a significant transmission risk due to close proximity to the oral cavity and aerosol generation. Saliva has been identified as a potential reservoir for SARS-CoV-2. Therefore, reducing viral load in saliva prior to dental treatment may reduce the risk of cross-infection.

Several antiseptic mouth rinses have been proposed as preprocedural interventions to reduce viral load in the oral cavity. This study evaluates and compares the short-term effects of chlorhexidine (in both rinse and lozenge forms) and povidone-iodine mouth rinse on salivary viral load in confirmed COVID-19 patients.

2. Objectives

Primary Objective

- To evaluate the short-term efficacy of different mouth rinses and lozenges (chlorhexidine rinse, chlorhexidine lozenges, and povidone iodine rinse) in reducing salivary SARS-CoV-2 viral load.

Secondary Objective

- To compare each intervention with saline as a control.
- To assess changes in viral load using Ct values of E and S genes via RT-PCR.

Material and methods:

3. Study Design

- This study is a **four-arm, open-label, randomized controlled clinical trial** designed to evaluate the short-term efficacy of three oral antiseptic interventions—chlorhexidine digluconate mouth rinse, chlorhexidine digluconate lozenges, and povidone-iodine (PVP-

I) mouth rinse—compared to a saline control in reducing salivary SARS-CoV-2 viral load in COVID-19-positive patients.

- **Type of Study:** Open-label, randomized controlled clinical trial
- **Study Setting:** King Fahad General Hospital and Al-Hamra Community Health Center, Jeddah, Saudi Arabia
- **Registration:** ClinicalTrials.gov (NCT04941131)
- **Ethical Approval:** Jeddah Health Affairs (#1485)

Study Design

Randomization and Blinding

- **Randomization:** Participants will be allocated using a simple 1:1:1:1 randomization schedule generated via computer-based random number sequencing.
- **Allocation Concealment:** Allocation will be performed using sealed opaque envelopes.

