- **Blinding:** This is an open-label study due to the obvious physical and functional differences between interventions (rinse vs. lozenge), which preclude participant and clinician blinding. However, the **laboratory personnel and statisticians will be blinded** to group allocation.

4. Participants

Inclusion Criteria:

- Adults aged ≥ 18 years
- Positive nasopharyngeal RT-PCR for SARS-CoV-2
- Ability to provide informed consent

Exclusion Criteria:

- Known allergy to study substances (chlorhexidine or povidone-iodine)
- Pregnancy

- Prior COVID-19 treatment
- Severe oral lesions that contraindicate rinse use

5. Interventions

Participants were randomized into four arms:

1. Chlorhexidine Mouth Rinse (CHX):

10 mL undiluted solution, used for 30 seconds.

2. Chlorhexidine Lozenges (CHX Lozenges):

2 mg lozenge to dissolve slowly in the mouth.

3. Povidone Iodine Mouth Rinse (PVP-I):

10 mL undiluted solution, used for 30 seconds.

4. Control (Saline):

10 mL normal saline rinse, used for 30 seconds.

All participants were instructed to refrain from eating, drinking, or oral hygiene procedures for at least 30 minutes before the intervention.

6. Sample Collection and Laboratory Testing

- **Saliva Collection:** Passive drool technique; 3 mL of saliva collected before and after intervention (5 minutes apart).
- **Analysis Method:**

Real-time RT-PCR using LabGun COVID-19 Kit (Biosewoom, Korea).

- Targets: E gene and S gene
- Measurement: Threshold cycle (Ct) values

7. Sample Size Calculation

- **Software:** G*Power 3.1
- **Effect size:** 1.1
- **Power:** 80%
- **Alpha:** 0.05
- **Required Sample:** 15 participants per group (Total N = 60)

Sample Size Justification:

- Based on an expected moderate-to-large effect size (Cohen's $f = 0.4$), $\alpha = 0.05$, power = 0.80, and four groups:
 - **Required sample = 60 participants (15 per group)**
 - Power calculation was performed using **G*Power 3.1**.
- To account for 10% attrition, **a total of 66 participants will be recruited**.

8. Statistical Analysis

Statistical Analysis

Software:

- Data will be analyzed using **IBM SPSS Statistics version 25** and **R (v4.3 or later)** for confirmatory and exploratory analyses.

Analysis Population:

- **Intention-to-treat (ITT):** All randomized participants will be included in the primary analysis, with imputation for missing data.

Primary Outcome Analysis:

- **Primary Endpoint:**

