 - Change in **Ct value** of SARS-CoV-2 E and S genes from baseline to post-intervention (ΔCt).

- **Between-Group Comparison:**
 - **One-way ANOVA** to assess differences in mean ΔCt across all four groups.
 - **Post-hoc Bonferroni test** for pairwise comparisons.
 - If assumptions of ANOVA are violated, **Kruskal–Wallis test with Dunn’s test** for post-hoc comparisons will be used.
- **Within-Group Comparison:**
 - **Paired t-test** to compare pre- and post-intervention Ct values within each group.
 - **Wilcoxon signed-rank test** will be used if normality is not met.

Assumptions and Validation:

- **Normality:** Assessed using **Shapiro-Wilk test** and QQ plots.
- **Homogeneity of variance:** Evaluated using **Levene’s test**.
- **Effect Size Reporting:** Partial η^2 for ANOVA, Cohen’s d for t-tests.

Missing Data Handling:

- For the ITT analysis, missing outcome data will be handled using **multiple imputation** (MI) under the assumption of missing at random (MAR).
- Sensitivity analyses using **last observation carried forward (LOCF)** will be conducted to assess the robustness of findings.

9. Expected Outcomes

- Povidone-iodine rinse will demonstrate the highest reduction in viral load.
- Chlorhexidine lozenges may show moderate efficacy.
- Chlorhexidine rinse may show variable outcomes.
- Control (saline) is expected to have no significant effect.

10. Ethical Considerations

- All participants provided informed written consent.
- Ethical approval was secured from local ethics board.
- All data were anonymized and securely stored.
- Participants had the right to withdraw at any time without consequences.

11. Timeline

Phase	Duration
Ethical Approval	Completed
Participant Recruitment	2 months
Data Collection	2 months
Laboratory Analysis	Concurrent
Data Analysis & Manuscript	1 month

12. Dissemination Plan

The study results will be disseminated through:

- Peer-reviewed publication
- Scientific conferences
- Institutional and ministry health updates

References

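### Efficiency improvement, not an error: the primary ΔCt ANOVA fixes the baseline slope at 1, and an ANCOVA on the baseline Ct already collected would generally be more precise for one degree of freedom

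*Combined protocol and SAP*

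**What the plan says.** Section 8 defines the primary endpoint as "Change in Ct value of SARS-CoV-2 E and S genes from baseline to post-intervention (ΔCt"). The between-group test is a "One-way ANOVA to assess differences in mean ΔCt across all four groups", followed by a "Post-hoc Bonferroni test for pairwise comparisons". The fallback, introduced by "If assumptions of ANOVA are violated", is Kruskal-Wallis with Dunn's test. None of these carries a covariate, and no baseline-adjusted model appears elsewhere in the document.

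The covariate is already planned. Section 6 has "3 mL of saliva collected before and after intervention (5 minutes apart"), so every ΔCt needs a baseline Ct. Section 2 lists as a secondary objective "To compare each intervention with saline as a control". Section 7 plans 15 participants per arm (60 in all, 66 recruited) and gives two effect sizes: "Effect size: 1.1", with no metric named, and Cohen's f = 0.4, introduced by "Based on an expected moderate-to-large effect size". It gives no SD of Ct and no pre/post correlation.

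**The concern.** A change-score ANOVA is an ANCOVA whose baseline slope is set to 1 instead of estimated. If the true slope is not 1, part of the baseline variation stays in ΔCt as noise. Chance baseline differences between arms, which are realistic with simple randomization and about 15 per arm, are then over- or under-corrected in any one trial, although they average out over randomizations.

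What is at stake is precision, not validity. The saline contrasts rest on two arms of about 15 and are Bonferroni-adjusted. Baseline adjustment could sharpen them without another participant.

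**Working it through.** **Inputs from the document.** Four arms, 15 each, N = 60, alpha 0.05, f = 0.4 or 1.1 (section 7).

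**Assumptions.** r (pre/post correlation) and k (post/pre SD ratio) are unknown, so they are varied. Unless stated, k = 1, with one slope and one residual variance in all arms. Effect sizes are in ΔCt SD units. The Bonferroni family is taken as all six pairs, and 1.1 is read as a standardized difference between two arms.

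**The plan's own figure.** With f = 0.4, the noncentrality is 60 × 0.16 = 9.6 on (3, 56) df, which gives power 0.709; 80% would need 76 participants (19 per arm). Fifteen per arm does follow from d = 1.1 in an unadjusted two-sided two-sample t test (power 0.828). That mismatch is a separate matter. The baseline for comparison here is 0.709.

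**Variance ratio.** With baseline variance 1, Var(ΔCt) = 1 + k² − 2rk, and the residual variance after regression on baseline is k²(1 − r²). Hence

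ratio = k²(1 − r²) / (1 + k² − 2rk), which is (1 + r)/2 at k = 1.

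Estimating the slope multiplies this by 1 + 1/(60 − 4 − 2) = 55/54 = 1.0185. The change in standard error is √(ratio × 1.0185) − 1. For r = 0.5: 0.75 × 1.0185 = 0.764, √0.764 = 0.874, a fall of 12.6%.

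**Power.** Omnibus: noncentral F with noncentrality 9.6/(ratio × 1.0185) on (3, 55) df. Pairwise: noncentral t with d√(7.5/(ratio × 1.0185)), two-sided alpha 0.05/6, 55 df (56 as planned). Reading f = 0.4 as one arm apart from three equal arms gives d = 0.4/√(3/16) = 0.924.

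| Analysis (k = 1) | Ratio × 55/54 | Standard error | Omnibus, f = 0.4 | Pair, d = 1.1 | Pair, d = 0.924 |
|---|---|---|---|---|---|
| Planned ΔCt | 1 | reference | 0.71 | 0.61 | 0.43 |
| ANCOVA, r = 0.5 | 0.764 | −12.6% | 0.83 | 0.76 | 0.57 |
| ANCOVA, r = 0.7 | 0.866 | −7.0% | 0.78 | 0.69 | 0.50 |
| ANCOVA, r = 0.9 | 0.968 | −1.6% | 0.72 | 0.63 | 0.44 |
| ANCOVA, r = 0.95 | 0.993 | −0.3% | 0.71 | 0.61 | 0.43 |
| ANCOVA, slope exactly 1 | 1.0185 | +0.9% | 0.70 | 0.60 | 0.42 |

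Break-even at k = 1 is r = 2/1.0185 − 1 = 0.96. Simulation with 20,000 trials per setting gave variance ratios of 0.765, 0.859, 0.968 and 0.993 at these four values of r.

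**Unequal SDs.** The slope is rk, so r alone does not settle the gain. At k = 1.2, omnibus ANCOVA power is 0.76 (r = 0.5), 0.72 (0.7) and 0.70 (0.8). At k = 0.8 it is 0.92 (r = 0.5) and 0.90 (0.7). At r = 0.95 the standard error falls 27% with k = 0.8 and 5% with k = 1.2.

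**Unequal slopes** (simulation, baseline SD 1; slopes assumed for saline, chlorhexidine rinse, PVP-I and lozenge). Change in standard error against ΔCt for each contrast with saline:

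| Slopes (residual SD) | Model | CHX rinse | PVP-I | Lozenge |
|---|---|---|---|---|
| 1, 1, 0.5, 0.75 (0.5) | ANCOVA | +7.7% | −7.2% | −0.9% |
| | with arm-by-baseline terms | +3.1% | −10.9% | −1.3% |
| 1, 1, 0.4, 0.6 (0.6) | ANCOVA | +9.4% | −7.2% | −3.5% |
| | with arm-by-baseline terms | +3.3% | −10.2% | −4.5% |

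In the first case, an unadjusted 5% test of PVP-I against saline has type I error 6.7% with ΔCt and pooled variance, 6.0% with model-based ANCOVA and 4.4% with HC3. With a common slope, HC3 costs about 4 points of pairwise power (0.72 against 0.76 at r = 0.5; 0.65 against 0.69 at r = 0.7).

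**Rank fallback** (20,000 runs, normal errors, f = 0.4), power at r = 0.5, 0.7, 0.9 and 0.95:
- Kruskal-Wallis on ΔCt: 0.67, 0.68, 0.67, 0.67.
- Kruskal-Wallis on residuals of ΔCt regressed on baseline: 0.80, 0.75, 0.69, 0.67.
- Ranked ANCOVA: 0.80, 0.73, 0.62, 0.59.

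Null rejection for the residual version was 4.4% to 4.9% across normal, t(3) and exponential errors, and 4.7% to 5.0% with unequal slopes.

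**The case against.** The strongest reply is that nothing is broken: the ΔCt ANOVA matches the stated endpoint, uses baseline and is unbiased. With samples 5 minutes apart, r may be high, and at r = 0.9 or above with equal SDs the gain is 1.6% or less in standard error. At k = 1.2 and r = 0.8, ANCOVA is marginally worse. All of this stands, and it is why no specific gain can be promised. It does not justify fixing the slope at 1, because the documents give neither r nor k, and high r with unequal SDs can still leave a useful gain.

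The power figures also depend on readings the document leaves open. If f = 0.4 is in units of the raw Ct SD (k = 1), planned omnibus power is already 0.92 at r = 0.7 (ANCOVA 0.95) and above 0.999 at r = 0.9. If only the three saline contrasts are Bonferroni-adjusted, planned power at d = 1.1 is 0.71, and ANCOVA gives 0.83, 0.78, 0.72 and 0.71 at the four values of r. The scale changes how much power there is to gain; the standard-error ratios do not change.

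Unequal slopes can cost the chlorhexidine-rinse contrast, part of a named objective, 8% to 9% in standard error. That cost is real, and it is the reason for the arm-by-baseline sensitivity model.

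Timing may limit the change. Sections 5 and 10 are partly in the past tense, although section 8 is in the future tense. The sponsor needs to confirm that outcome data are unseen.

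**Conclusion.** The point holds as an efficiency improvement that should be made; it is not an error in the plan. With a common slope and residual variance the trade is lopsided: at worst a 0.9% larger standard error (about one point of power), against a 12.6% smaller one at r = 0.5 and equal SDs, worth 12 points of omnibus power (0.71 to 0.83) and 15 of pairwise power (0.61 to 0.76). The gain is nil at r of about 0.96 with equal SDs. If slopes differ between arms, one contrast can lose while others gain.

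Confidence in the size of the benefit is only medium, because r, k and the effect-size scale are assumptions. ANCOVA does not reconcile the two effect sizes in section 7: at f = 0.4 on the ΔCt scale with equal SDs, 60 participants reach 80% power only if r is about 0.6 or lower.

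**What to change.** Before outcome data are seen, amend section 8 as follows.

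- **Primary model.** For each gene, ANCOVA of post-intervention Ct (or, equivalently, ΔCt) on arm and that gene's baseline Ct, with model-based standard errors.
- **Contrasts.** Report adjusted pairwise differences, including each arm against saline, with confidence intervals that keep the planned Bonferroni adjustment.
- **Fallback.** If residual assumptions fail, run the planned Kruskal-Wallis and Dunn tests on the residuals of ΔCt regressed on baseline Ct, all arms pooled. Ranked ANCOVA is a valid alternative, but in simulation it fell below the unadjusted test at r = 0.9.
- **Sensitivity analyses.** The planned ΔCt ANOVA, and an ANCOVA with arm-by-baseline terms (baseline centred) or HC3 errors in case slopes or variances differ.

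If outcome data have already been seen, ANCOVA should be added only as a clearly labelled sensitivity analysis.

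The cost is a short SAP paragraph and one degree of freedom, with no new samples or participants. SPSS and R, both already named, fit these models. How undetected salivary Ct is handled affects both analyses and needs its own rule.

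### Bonferroni over all six pairs of arms is valid but inefficient: the listed objectives name only three antiseptic-versus-saline contrasts, and testing those alone would gain about 5 to 11 points of power.

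*Combined protocol and SAP*

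**What the plan says.** - **Section 8, Between-Group Comparison:** a one-way ANOVA of mean Ct change "across all four groups", followed by a "Post-hoc Bonferroni test" on the pairwise comparisons. If the ANOVA assumptions fail, Kruskal–Wallis with Dunn's test takes over. The text does not restrict the pairs, give their number, or say whether a significant ANOVA is required before the pairwise tests.
- **Section 2, Secondary Objective:** "To compare each intervention with saline as a control". The primary objective names no pair of arms. Section 3 also describes the three antiseptics as set against a saline control.
- **Sections 1 and 9:** the background speaks of comparing the chlorhexidine forms and povidone-iodine, and the expected outcomes rank povidone-iodine first. Both imply interest in antiseptic-versus-antiseptic differences, although no listed objective names one.
- **Section 7:** "Effect size: 1.1", 80% power, alpha 0.05, and "Required Sample: 15 participants per group (Total N = 60"). The same section also justifies N = 60 by Cohen's f = 0.4 for four groups.
- **Section 8, Primary Endpoint:** change in Ct of the E and S genes, with no rule for combining the two.

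**The concern.** The family that is adjusted for is twice as large as the family that the objectives name. Four arms give six pairs: three against saline and three between antiseptics. At 0.05/6 per pair, half of the 5% is spent on pairs outside the listed objectives.

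With 15 per arm this matters. The plan's two-group calculation reaches 80% only for a single unadjusted comparison, and any multiplicity adjustment lowers the chance of showing that an antiseptic beats saline. A family matched to the objective, or a sharper procedure on the same six pairs, recovers part of that loss with no extra participants and the same family-wise error.

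**Working it through.** **Inputs.** From section 7: 15 per arm, alpha 0.05, effect size 1.1. From section 3: a "simple 1:1:1:1 randomization schedule", here taken to give equal arms. ANOVA error df = 60 − 4 = 56.

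**Assumptions the plan does not state.** The 1.1 is Cohen's d for an antiseptic–saline difference, and alpha is two-sided.

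**Step 1: the plan's own figure.** For a two-sample t-test with d = 1.1, the noncentrality is 1.1 × √(n/2). Power is 79.99% at n = 14 and 82.8% at n = 15, so the smallest n reaching 80% is 15. This reproduces the stated size and supports reading 1.1 as d. The other stated basis does not reproduce: f = 0.4 with four groups and N = 60 gives 70.9% for the ANOVA, and 80% with equal arms needs N = 76.

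**Step 2: alpha share.** Pairs = 4 × 3 / 2 = 6. Alpha per pair = 0.05/6 = 0.00833. The three antiseptic pairs take 3 × 0.00833 = 0.025, half of 0.05.

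**Step 3: power per saline contrast, one gene, no ANOVA gate.** Noncentrality = d × √(15/2), which is 3.012 at d = 1.1. Power = P(|T| > c), with T noncentral t on 56 df.

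| Procedure | Critical value c | d = 1.1 | d = 1.0 | d = 0.8 |
|---|---|---|---|---|
| Bonferroni, six pairs | 2.735 | 61.0% | 50.6% | 30.3% |
| Tukey, six pairs | 2.648 | 64.3% | 54.0% | 33.3% |
| Bonferroni, three contrasts | 2.468 | 70.6% | 60.8% | 39.8% |
| Dunnett, three contrasts | 2.414 | 72.4% | 62.8% | 41.8% |

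At d = 1.1, Dunnett gains 72.4 − 61.0 = 11.4 points. Of these, 70.6 − 61.0 = 9.6 come from reducing the family to three and 72.4 − 70.6 = 1.8 from Dunnett itself. Tukey on all six gains 64.3 − 61.0 = 3.3.

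**Step 4: with a significant ANOVA required first.** Simulated at 15 per arm for the contrast whose true difference is 1.1, with the gate applied to every procedure:

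| True arm means in SD units (saline first) | Bonferroni, six | Tukey, six | Dunnett, three | Dunnett gain |
|---|---|---|---|---|
| 0, 1.1, 1.1, 1.1 | 60.9% | 63.9% | 70.8% | 9.9 |
| 0, 0, 0, 1.1 | 60.8% | 63.9% | 70.8% | 10.0 |
| 0, 0.37, 0.73, 1.1 | 60.4% | 62.7% | 67.1% | 6.7 |
| 0, 0.55, 0.55, 1.1 | 60.0% | 61.9% | 65.0% | 5.0 |

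Dunnett gains about 5 to 10 points and Tukey about 2 to 3.

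**Step 5: two genes.** If alpha is split, each gene is tested at 0.025. Dunnett's critical value becomes 2.696 and power at d = 1.1 falls to 62.5%. Six-pair Bonferroni on the same footing uses 0.05/12 = 0.00417 per test, critical value 2.988, and falls to 51.5%. The gap stays at 62.5 − 51.5 = 11.0 points, but 72% is then out of reach.

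**The case against.** The strongest reply is that nothing here is wrong. All-pairs Bonferroni after an ANOVA controls the family-wise error for one outcome, and the antiseptic pairs have a purpose: the background speaks of comparing the products, and ranking povidone-iodine first can be tested only with those pairs. If all six are wanted, Bonferroni costs only about 2 to 3 points against Tukey. All of this stands. It limits the point to efficiency and alignment.

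Four stronger readings are tempting, and the documents do not support them:

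- **The antiseptic pairs are of no interest to the trial.** Sections 1 and 9 say otherwise. What holds is that no listed objective names them. The saline comparison is itself listed as secondary, although section 3 frames the design around it.
- **Bonferroni is the most conservative choice available.** Scheffé's method is more so: critical value 2.882 and 55.5% power at d = 1.1.
- **The trial already misses 80% on the effect size used here.** At d = 1.1 a single unadjusted comparison has 82.8%. The shortfall before adjustment comes only from the f = 0.4 basis (70.9%).
- **The loss is a fixed 11 points.** That is close to the upper end at d = 1.1 and holds only if the contrasts do not depend on the ANOVA. Section 8 calls the tests post-hoc without saying whether they are gated, so the range has to be given.

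**Conclusion.** The point holds as an inexpensive improvement to a valid plan. At d = 1.1, testing only the three saline contrasts with Dunnett raises power per contrast from about 61% to 72% without an ANOVA gate, a gain of about 11 points. With a gate the gain is about 5 to 10. Keeping six pairs and replacing Bonferroni with Tukey gains about 2 to 3.

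The figures assume that 1.1 is Cohen's d for antiseptic versus saline, two-sided alpha, 15 analysed per arm, equal variances, and one gene. If alpha is split across the two genes, Dunnett gives about 62%. Simple randomization may leave the arms somewhat unequal. Recruiting 66 ("To account for 10% attrition") gives 66/4 = 16.5 per arm if nobody is lost, where six-pair Bonferroni has 66.7% and Bonferroni over three has 75.6%, a similar gap. None of the options reaches 80% at 15 per arm, so the change narrows the shortfall but does not remove it.

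**What to change.** In section 8:

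1. Name the three antiseptic-versus-saline contrasts of mean Ct change as the confirmatory family. Test them with Dunnett's procedure at a two-sided family-wise 5%, and report each as a difference in cycles with a simultaneous 95% confidence interval.
2. State that these contrasts do not depend on a significant ANOVA.
3. Label the three antiseptic-versus-antiseptic pairs secondary.
4. Restrict the Dunn fallback to the same three contrasts, with its own stated adjustment.
5. State how the E and S genes are combined: one primary gene, a requirement on both, or a split of alpha.

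If the sponsor wants the antiseptic pairs to be confirmatory, add them to section 2 and use Tukey over all six. Holm is also possible, but it does not directly give simultaneous intervals.

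The cost is wording only. Under the Dunnett option the antiseptic pairs lose confirmatory status, including the test of whether povidone-iodine ranks first. Under the Tukey option nothing of substance is lost, but the gain is small.

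### With one sample before and one after treatment, LOCF is a single no-change scenario and cannot show how far the MAR assumption must fail before a conclusion changes

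*Combined protocol and SAP*

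**What the plan says.** Section 6 schedules two samples per participant: "3 mL of saliva collected before and after intervention (5 minutes apart"). Section 8 defines the primary endpoint as the change in Ct of the E and S genes "from baseline to post-intervention (ΔCt") and uses one-way ANOVA "to assess differences in mean ΔCt across all four groups", followed by Bonferroni pairwise tests.

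On missing data, Section 8 (Analysis Population) states: "All randomized participants will be included in the primary analysis, with imputation for missing data". Under Missing Data Handling the method is multiple imputation "under the assumption of missing at random (MAR"). The only sensitivity analysis named is: "Sensitivity analyses using last observation carried forward (LOCF) will be conducted to assess the robustness of findings".

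Section 7 allows for 10% attrition, recruiting 66 to retain 60. Section 10 adds: "Participants had the right to withdraw at any time without consequences". The trial is open-label for participants and clinicians.

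**The concern.** LOCF is normally discussed for trials with several visits, where the carried value is some intermediate measurement. Here there is no intermediate measurement. If the second sample is missing, the only value to carry is the baseline, and the endpoint becomes zero by construction.

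The point concerns second samples that do not exist (withdrawal, refusal, too little saliva), not samples that were tested and failed to amplify.

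Three consequences follow:

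- The check is one fixed scenario. It does not vary the departure from MAR, so it cannot locate the point at which a conclusion changes.
- The zeros enter as observed data, with no imputation uncertainty.
- Each arm's mean ΔCt is multiplied by that arm's own completion rate. Contrasts with saline shrink when losses fall in the antiseptic arm. Contrasts between antiseptics tilt towards the arm with fewer losses.

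The last matters because the plan compares all pairs of arms, and Section 9 predicts a ranking among the antiseptics.

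**Working it through.** **Inputs from the plan.** Two samples, ΔCt as endpoint, ANOVA then Bonferroni (Sections 6 and 8); effect size 1.1, 15 per group, 66 recruited, 10% attrition (Section 7); saline expected to have no significant effect (Section 9). Four arms give six pairwise comparisons, so the nominal level per pair is 0.05/6 = 0.83%. Recruitment gives 66/4 = 16.5 per arm; 16 is used.

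**The plan's own figure.** A two-sample t-test with a standardized difference of 1.1, two-sided 0.05 and 80% power needs 15 per group (power 0.828 at 15, just under 0.80 at 14). This reproduces 60 in total, so 1.1 is read here as a standardized difference. The other effect size in Section 7, Cohen's f = 0.4, does not give 60 (it needs 19 per group); that is a separate matter.

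**Assumptions not in the plan.** SD of ΔCt = 1; positive ΔCt means less virus; losses random within arm; true mean 1.1 or 2 SD in all three antiseptic arms and 0 on saline; the split of losses.

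**Expected value under LOCF.** With true mean μ and missing share m, post = pre for those missing, so the expected arm mean is μ(1 − m). Two equally effective arms then differ by μ(m₂ − m₁).

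- Antiseptic with 3 of 16 missing, saline with none: 1.1 × 13/16 = 0.89, against a true 1.1.
- Two equal antiseptics, 0 and 3 of 16 missing: 1.1 × 3/16 = 0.21 SD, against a true 0. At 2 SD: 2 × 3/16 = 0.375.
- If μ = 0, or the missing shares are equal, no difference is created.

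**Simulated false rejection between two equally effective antiseptics under LOCF** (four arms, saline at 0):

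| Losses in the two arms | μ | Six-comparison Bonferroni (nominal 0.83%) |
|---|---|---|
| 2 of 17 vs 1 of 16 | 1.1 | 0.6% |
| 0 vs 3 of 16 | 1.1 | about 1.6% |
| 0 vs 3 of 16 | 2.0 | about 3.6% |
| 0 of 17 vs 4 of 16 | 1.1 | 2.6% |
| 0 of 17 vs 6 of 16 | 1.1 | 5.8% |

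The rows with arms of 17 and 16 have 66 participants and 6 losses in all. Observed-data analysis stays at about the nominal level. Unadjusted two-arm t-tests for 0 versus 3 missing reject about 8% (1.1 SD) and 12% (2 SD) of the time at nominal 5%, but those are not the pairwise tests the plan specifies.

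**Contrast with saline.** For 1.1 versus 0 with 3 of 16 missing in the antiseptic arm, an unadjusted two-sided t-test has 70% power under LOCF and 81% on observed data.

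**Loss of uncertainty.** If all six losses are on saline and the antiseptics are at 1.1 SD, the ANOVA rejects 94% of the time under LOCF and 73% on observed data. With saline truly at 0 the saline mean is not biased. The gain comes from six exact zeros being treated as measurements.

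**The case against.** The strongest reply is that LOCF does depart from MAR. It supposes that those lost had no change, which is pessimistic for an antiseptic compared with saline when the losses are in the antiseptic arm. A conclusion that survives has survived one unfavourable scenario. That scenario also lies near the far end of the delta grid proposed below, apart from having no residual variance. This stands. A reader might infer that LOCF says nothing at all about MAR; the documents do not support that. What it lacks is a graded departure and honest uncertainty.

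The size is also open to challenge. Ten percent attrition is about 1.6 losses per arm of 16. If losses are independent at that rate, a given pair of arms differs by 3 or more only about 13% of the time. Samples are 5 minutes apart, which leaves little time for arm-dependent dropout, and the documents give no evidence that it would occur. Open-label delivery makes unequal loss possible, not expected. A reader might take the 8% and 12% rates as the plan's error rates; under its Bonferroni procedure they are about 1.6% and 3.6%.

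A reader might also infer that LOCF cannot cover the ITT set, because someone who withdraws before baseline has nothing to carry forward. The plan does not say whether baseline saliva is taken before or after randomization, so this gap may never arise.

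Finally, LOCF is only a sensitivity analysis. It does not alter the primary multiple-imputation result, and nothing here shows that result to be biased.

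**Conclusion.** The point holds as a minor one. That LOCF fixes ΔCt at zero follows from the two-sample design and needs no assumption. It follows equally that one fixed value cannot show how far MAR must fail before a conclusion changes, although that is the question a robustness check on MAR should answer.

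The numerical harm is conditional. It needs a non-zero mean ΔCt and unequal losses. At 0 versus 3 missing in arms of 16 it roughly doubles the Bonferroni-level false rejection between equal antiseptics at 1.1 SD (about 1.6% against 0.83%), and more than quadruples it at 2 SD (about 3.6%). With near-balanced losses there is no inflation. The SD, the true means and the loss split are assumptions; the plan supplies only the 1.1, the arm sizes and the overall attrition.

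**What to change.** In Section 8, Missing Data Handling, replace LOCF as the robustness check with delta-adjusted multiple imputation:

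- For each antiseptic-versus-saline contrast, shift the imputed ΔCt in the antiseptic arm downward (towards less benefit) in fixed steps, from 0 to the full observed effect, leaving saline unshifted. Report the shift at which the conclusion changes.
- For antiseptic-versus-antiseptic contrasts, vary the shift separately by arm.
- Report missing second samples by arm, so that the reader can judge whether the larger shifts matter.

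An analysis of participants with both samples may be added as a supplementary description. It also treats missingness as ignorable, so it should not be presented as a test of MAR.

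The cost is a change to the SAP wording, a few lines of R (already among the planned software) and a small table in place of one result. No study procedure changes.
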